4.1 Inclusion Criteria

- Child is a patient at Erie Family Health Center
- Child is age 5-16 at the start of the study
- Child lives with the index caregiver at least 5 days out of the week

- Child has uncontrolled asthma.¹³ This is defined as a score of 1.25 or greater on the Asthma Control Questionnaire,¹⁴⁻¹⁷ a score of less than 20 on the Asthma Control Test/childhood Asthma Control Test,²⁰⁻²⁴ or report of oral corticosteroid use at least once in the past year.¹³
- Family has a working telephone

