Participants that fail the screener or who chose to not provide informed consent will be thanked for their time. Participants that fail the screener but are interested in the study will be offered the option of being put on a re-contact list. If they agree to be put on this list, their contact information will be saved and research staff can call them again in several months to rescreen them. Personal identifying data from the screening (initial and re-contact lists) will be kept in a secure location until recruitment is ended, at which point it will be destroyed. (We will keep their name during the recruitment period only to prevent contacting people who have screened out.) All staff involved in recruitment will receive careful training about the study and the clinic services to ensure that everyone approached understands that participation is voluntary and services at Erie will continue regardless of study participation, and so that Erie staff understands their primary role is patient care. Recruitment will not impinge on clinical responsibilities or clinic operations. Staff involved in recruitment have their time covered by the study. Providers who refer the study to patients do so when they have time and feel comfortable only.

Randomization will be conducted in a 1:1 ratio using randomly mixed permuted blocks of size 4 and 6 to ensure reasonably equal allocation while reducing predictability of the assignment sequence. Upon completion of the randomization assignment, the data management team will generate a letter to the participant informing him/her of their study status and also notify the Erie Intervention Coordinator who will assign the patient to a CHW if randomized to that arm. Although double blinding in a behavioral randomized clinical trial is impossible, blinding will be maximized by: 1) incomplete disclosure of study goals for participants during consent (see Human Subjects for details), 2) blinding outcomes assessors; 3) incomplete disclosure of research hypotheses for non-investigators staff; and 4) training co-investigators and staff in the concept of equipoise. Intervention investigators and staff will be unblinded to treatment arm because they will need to work with the CHWs and monitor intervention fidelity and data accuracy. Study staff and investigators (with the exception of the Safety Officer) will not have access to interim outcomes data.

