9.0 Data Analysis

All analyses will be performed by the investigators and analysts in the Institute for Health Research and Policy using SAS version 9.4. We will compare key population descriptors in the two treatment groups as patient recruitment progresses (at N=100 and N=150) to ensure that the randomization process is achieving reasonable balance, being careful to protect operational staff from bias. Basic summary statistics will be calculated for outcome variables and covariates. Continuous variables will be assessed for normality using Q-Q plots and compared using 2-sample t-tests. If distributions are sufficiently non-normal, then a suitable transformation or non-parametric test will be used. Categorical variables will be compared using chi-square tests. Significance tests will be two-sided at level $\alpha=0.05$.

Specific Aim 1: To assess the efficacy of the integrated CHW home asthma intervention relative to the AE-C intervention at 12-months post-randomization as demonstrated by asthma control. This study will employ two primary measures of asthma control: number of days with activity limitation over the previous 14 days and the Asthma Control Test/childhood Asthma Control Test (ACT/cACT). The mean total number of days with activity limitation over the previous 14-day period will be assessed at 12-months between the two treatment arms using the two-sample t-test or Mann-Whitney test. If the mean days with activity limitation in the intervention arm is at least 30% lower than that of the AE-C arm and $p < 0.05$, we will conclude that the CHW intervention is more effective. The ACT/cACT will be analyzed using similar methods; a MID of 0.2 will be used to determine intervention efficacy. Linear mixed models will

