then be employed to analyze primary outcomes at twelve months. To test the CHW intervention's efficacy on these outcomes, we will first conduct per protocol analyses limited to those patients who received CHW intervention. We will correct potential selection bias by including covariates found to be differentially related to nonadherence. Under the missing at random (MAR) assumption, this ensures unbiased estimates from linear mixed models. Additionally, to test the intervention's effectiveness in clinical practice we will conduct intention-to-treat analyses that include outcomes for all patients randomized. Nonadherent and other subgroups of patients can be expected to exhibit differentially higher rates of missing data. We will therefore examine the sensitivity of inferences to multiple imputation rule using the SAS macros of Little and Yau (1996), including last observation carried forward (LOCF), return to baseline, and continuing on apparent trajectory. The fixed-effects part of the model will be $Days_{ij} = \beta_0 + \beta_1 Time_{ij} + \beta_2 Tx_i + \beta_3 (Tx_i * Time_{ij}) + \epsilon_{ij}$, for subject i at visit j . Candidate covariance structures will be assessed using the data's correlation structure and Akaike's Information Criterion (AIC). A random intercept will be included in the model if it significantly improves the model fit as determined by the likelihood ratio test. Standardized residuals and Cook's distance will be used to assess the influence of outliers and individual observations and residual plots will be used to check the multivariate normal distribution assumption. These analyses will be conducted in SAS PROC MIXED (and PROC GLIMMIX for categorical outcomes), and will be followed by an exploratory variable selection analysis in PROC GLMSELECT. Potentially confounding covariates will be considered for model inclusion using the least absolute shrinkage and selection operator (LASSO) model selection method. This method identifies a significant subgroup of covariates that will form a more parsimonious model. The LASSO method avoids problems typically encountered using stepwise procedures. To accommodate potential age-specific effects, heterogeneity of treatment effects by age will be examined as an exploratory analysis.

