12.0 Statistical Considerations

Statistical analysis is described in Section 9.0. The sample size for the study was determined to allow assessment of the relative efficacy of the proposed interventions with respect to asthma control. While a strong clinical definition of asthma control has been in place for some time, there is no gold standard for assessing asthma control. The Asthma Control Questionnaire (ACQ) has been validated in diverse, large samples but currently there is an absence of substantive data on this test (data such as variability and reasonable effect sizes within this target population) upon which statistical power and sample size estimates can be based. Therefore we have conducted two calculations to ensure adequate power. Using the ACQ, a sample size of 100 per group (total N=200) had power 0.87 to detect the minimally important difference (MID) of 0.5 established for this test.¹⁴ We performed a separate power calculation using number of days with activity limitation (over the past 14-days) as Zeiger et al.⁴² found "activity limitation" to be a strong determinant of the composite asthma control score. In a multi-site inner-city (including Chicago) randomized trial of a home CHW asthma intervention, Morgan et al. reported activity limitations over the previous 14 day period.⁴³ Based on their data, we hypothesize a mean of 3.9 "activity limitation" days at baseline in both groups (SE 0.22) and, in the AE-C comparison group, a mean at 12 months of 2.84 days (SE 0.10). We anticipate the proposed CHW intervention will be more potent than that tested by Morgan et al. because it involves a higher dose and more physician involvement. Within the proposed CHW home intervention group, we anticipate a mean of 2 "activity limitation" days over a 14-day period at 12 months (SE 0.10), representing a 30% reduction from the AE-C comparison group (and 50% reduction from the baseline mean). Further assuming an attrition rate of 15% and 80% power, the standard two-group t-test for comparing means (at 12 months) requires a sample size of about 111 per group, for a total of 223 participants. Analyses to examine heterogeneity of treatment effects by age, race, or other groups have more limited power but results will be considered suggestive for further research.

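### The plan does not say how the two ACT/cACT forms are put on one scale, and the primary comparison is not adjusted for form

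*Combined protocol and SAP*

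**What the plan says.** Section 9.0, Specific Aim 1, states: "This study will employ two primary measures of asthma control: number of days with activity limitation over the previous 14 days". The second of the two measures is the ACT/cACT, named as a single measure. Its analysis takes one sentence: "The ACT/cACT will be analyzed using similar methods; a MID of 0.2 will be used to determine intervention efficacy". The methods referred to are the two-sample t-test or Mann-Whitney test at 12 months, followed by a linear mixed model whose fixed effects are time, treatment and their interaction.

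The instrument table in Section 6.8 gives the two forms one row, with an item count of 5-7. On age, Section 4.1 says: "Child is age 5-16 at the start of the study". No section says which child completes which form.

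The scale information is thin. Section 4.1 applies one eligibility cut-off to both forms, "a score of less than 20 on the Asthma Control Test/childhood Asthma Control Test". No section gives a scoring range, an SD, or a rule for combining the forms.

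Age and form play no part in allocation as described: "Randomization will be conducted in a 1:1 ratio using randomly mixed permuted blocks of size 4 and 6", with no strata stated. In the analysis, "heterogeneity of treatment effects by age will be examined as an exploratory analysis", and LASSO covariate selection is exploratory too. Neither mentions the form.

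**The concern.** Suppose two forms of different length have different average scores in comparable children. A pooled comparison that ignores form then carries the between-form difference as extra spread within each arm. That spread says nothing about treatment and can be removed at almost no cost. It falls on a primary outcome for which Section 12.0 gives no power calculation: its two calculations concern the ACQ and days with activity limitation.

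Two further points follow from the undefined scale. First, a threshold of 0.2 cannot be interpreted until the reader knows 0.2 of what, and for which form. Section 12.0 treats the ACQ's MID of 0.5 as belonging to that instrument, whereas Section 9.0 gives one value for two forms. Second, the same measures are used again in Specific Aim 2 (18 and 24 months) and, as change in asthma control, in the cost-effectiveness ratio of Specific Aim 3. If a child changes form during the 24 months, the shift in scale would enter that child's trajectory as if it were clinical change.

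**Working it through.** **Inputs from the documents.** Section 9.0: "Significance tests will be two-sided at level" 0.05. Section 12.0: "Further assuming an attrition rate of 15% and 80% power"; 12-month means of 2.84 and 2 days, a difference of 0.84; about 111 per group, 223 in total.

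**Inputs not in the documents, assumed here.** The mean offset between forms, r, in within-form SDs (0.25 to 1.0); the share of children on one form, w (0.3 to 0.7); equal within-form SDs.

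**1. The plan's own sample size.** There is none for ACT/cACT, so the days calculation serves only to fix the number of completers. Section 12.0 gives SEs but no SD, so 111 cannot be derived forward. Working backward with n = 2(z₀.₉₇₅ + z₀.₈₀)² SD² / 0.84², an SD of about 2.05 gives 2 × 7.849 × 4.2025 / 0.7056 = 93.5, so 94 per group. Then 94 / 0.85 = 110.6, so 111. I therefore use 94 completers per arm.

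**2. Added variance in the 12-month comparison.** With within-form variance set to 1, the variance of the pooled score within an arm is 1 + w(1 − w)r². A test that would have 80% power without the offset then has power Φ[(1.960 + 0.842)/√variance − 1.960].

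For r = 0.75 and w = 0.5: variance = 1 + 0.25 × 0.5625 = 1.141; 2.802/1.068 = 2.623; 2.623 − 1.960 = 0.663; Φ(0.663) = 0.746.

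| Offset r | Variance factor (w 0.3 to 0.7) | Completers per arm to match 94 | 80% power becomes |
|---|---|---|---|
| 0.25 SD | 1.013–1.016 | 96 | 79.4–79.5% |
| 0.5 SD | 1.052–1.062 | 99–100 | 77.6–78.0% |
| 0.75 SD | 1.118–1.141 | 106–108 | 74.6–75.5% |
| 1.0 SD | 1.21–1.25 | 114–118 | 70.7–72.1% |

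The 80% is a reference point, since the plan states no power for this outcome.

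**3. Where the inflation applies.** The formula describes the cross-sectional t-test. In the mixed model, a child who keeps one form carries a constant offset. A random intercept or within-child covariance, both contemplated in Section 9.0, largely removes that offset from the treatment-by-time estimate.

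**4. The 0.2 threshold.** With 94 per arm, the smallest observed difference that reaches p < 0.05 in the t-test is t₀.₉₇₅,₁₈₆ × SD × √(2/94) = 1.973 × 0.1459 × SD = 0.288 SD.

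- If 0.2 is in SD units, every significant difference already exceeds it.
- If 0.2 is in points, assumed SDs of 2, 3, 4 and 5 give smallest significant differences of 0.58, 0.86, 1.15 and 1.44 points, again all above it.
- The threshold could bind only if the SD were below 0.2/0.288 = 0.69 on whatever scale is used.

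**5. Change of form.** Section 4.1 gives ages 5-16 and Section 6.2 gives follow-up to 24 months, but there is no rule linking age to form. How many children would change form, if any, cannot be computed.

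**The case against.** The strongest reply is that the plan never says raw scores are pooled. A reader might infer it from the shared cut-off of 20 and the absence of any mention of standardization, but Section 9.0 does not state the scale. A value as small as 0.2 beside a cut-off of 20 could equally belong to a standardized or per-item score. Item count does not by itself fix the score range, and the common cut-off shows that the plan regards the forms as comparable for classification. This stands: the defect is that the method of combination is missing, not that a wrong one has been chosen. A shared cut-off does not, however, show that means or one-point differences agree between the forms.

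It can also be said that 1:1 randomization balances the mix of forms on average, that the mixed model absorbs most of a constant offset, and that form changes expected equally in both arms fall mainly on the time term. All of this is right. It removes any charge of expected bias and confines the precision loss mainly to the 12-month two-sample test. That test is nonetheless the first comparison named for this primary outcome.

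Finally, the LASSO and age analyses might pick up form indirectly. Both are exploratory and neither names it, so they do not define the primary comparison.

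**Conclusion.** The point holds as a gap in the specification of a primary outcome, with a modest and uncertain cost in precision. For offsets of 0.25 to 0.75 SD the loss is 1 to 14% in variance. It is material only towards the upper end, and nothing in the documents shows where the true offset lies. The range rests wholly on the assumed offset, the assumed mix of forms and equal within-form SDs.

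Two stronger conclusions are tempting and should not be drawn. One is that combining the forms makes the MID meaningless. If 0.2 were in within-form SD units, one value could serve both forms. It is uninterpretable as written chiefly because it has no unit or source, and on the readings checked it adds nothing to the p < 0.05 requirement. The other is that changes of form distort the longitudinal results. That is possible, but without an age rule it remains a conditional risk, not a demonstrated fault.

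**What to change.** - State which child gets which form, by a rule that does not depend on arm, and how each form is scored. Record the form used at every visit.
- Make the primary 12-month ACT/cACT comparison a model adjusted for form, and add form and form-by-visit terms to the mixed model. Alternatively, center and scale each form by its own baseline mean and SD, pooled over arms and held fixed at all visits. Restandardizing at each visit would erase the time trend that the mixed model is meant to estimate.
- Show the arm difference for each form as supportive. Do not average raw per-form differences by inverse variance unless the forms have first been put on a common scale.
- Give the MID a unit and a source: one value on the standardized scale, or one per form. A form term removes a mean offset but does not make a point on one form equal to a point on the other.

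The cost is one or two model terms, one recorded item per visit and a few sentences of text, with no extra participants or visits. The per-form estimates will be less precise than the combined one, which is why they should stay supportive. Cheap improvement.

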3.0 Objectives/Aims

Primary Aim 1: To assess the efficacy of the integrated CHW home asthma intervention, relative to clinic-based AE-C education over 12-months, as demonstrated by asthma control. We hypothesize that the CHW arm will have significantly greater asthma control than the AE-C arm at 12-months as measured by days with activity limitation over the previous 14 days and the Asthma Control Test/childhood Asthma Control Test.

Specific Aim 2: To assess maintenance of intervention efficacy, as demonstrated by asthma control at 18 and 24 months after randomization. We hypothesize that changes in efficacy outcomes will be maintained after cessation of the intervention.

Specific Aim 3: To determine the cost-effectiveness at 12-months of CHW and AE-C intervention delivery, and additional costs or savings related to asthma exacerbations at 12- and 24-months.

Specific Aim 4: To assess the efficacy of the integrated CHW home asthma intervention relative to clinic-based AE-C education, as demonstrated by asthma control, among those experiencing depression, stress, and/or post-traumatic stress disorder (PTSD). We hypothesize that among those living with depression, stress, and/or PTSD, the CHW intervention will be significantly more effective in achieving and maintaining asthma control than the AE-C education intervention.

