6.3. Treatment Arm: Pediatric Asthma CHW Home Intervention

The pediatric asthma CHW home intervention is modeled after that of Krieger et.al.¹⁹ and refined from Project CURA.

6.3.1 Asthma Home Visit Protocol and Topics: Families will be offered 10 home visits over 12 months. At the CHW home visits, CHWs will spend 1-2 hours with the family. CHWs will educate them on the “core curriculum.” The topics in the core curriculum are standard topics for asthma educators and are intended to reduce impairment (prevent chronic symptoms, infrequent use of quick relief medications, maintain normal activity levels) and reduce risk (prevent exacerbations, minimize emergency care, prevent reduced lung growth, and minimize adverse therapy effects).¹³ The CHWs will approach each visit with the intention to teach one or two of the core curriculum topics. Each visit will begin with several minutes of social discussion for the purpose of relationship building. Behavior change plans from the previous visit will be reviewed and discussed. Behavior change plans are small goals for a specific change over a several-week period. Examples include: “getting a prescription from my doctor” or “writing down

when my child coughs". The main portion of the visit will involve the education session around a core curriculum topic. When a CHW notes a barrier in the delivery of the education, he or she will then incorporate a relevant self-management skill. For example, the CHW may know that the family is not giving a medication as often as prescribed but instead of just saying that, the CHW will have the family track how often the child is receiving their medication (self-monitoring). The family will "self-discover" they do not give the medicine as often as recommended. Then the CHW will have the family problem solve as to why that might be (storage location, parent work schedules, medication fear, etc.). Once they have a list of the problems, the family will create a behavior change plan for one problem they want to solve.

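### Aim 1 efficacy is modelled first in an undefined set of CHW receivers; intention-to-treat is only additional, and neither mixed-model set is named primary

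*Combined protocol and SAP*

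**What the plan says.** Section 3.0 frames Primary Aim 1 as an efficacy aim: "To assess the efficacy of the integrated CHW home asthma intervention, relative to clinic-based AE-C education over 12-months".

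Section 9.0, Specific Aim 1, then gives two layers of analysis.

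- **Success rule.** Mean activity-limitation days "will be assessed at 12-months between the two treatment arms using the two-sample t-test or Mann-Whitney test". The conclusion in favour of CHW begins "If the mean days with activity limitation in the intervention arm is at least 30% lower than that of the AE-C arm" and also needs p < 0.05. No analysis set is named. Section 12.0 sizes the trial on this t-test.
- **Mixed models.** These follow. For efficacy, "we will first conduct per protocol analyses limited to those patients who received CHW intervention". On the exclusions: "We will correct potential selection bias by including covariates found to be differentially related to nonadherence". Then: "Under the missing at random (MAR) assumption, this ensures unbiased estimates from linear mixed models". For effectiveness in clinical practice, "we will conduct intention-to-treat analyses that include outcomes for all patients randomized", introduced as an addition.

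On receipt, Section 6.3.1 says "Families will be offered 10 home visits over 12 months". No section says how many visits count as having received the intervention. Section 6.4.2 describes AE-C sessions that also depend on the family coming to clinic, but gives no receipt rule for that arm. Section 6.6 has both CHWs and the AE-C document every encounter and foresees using those records to determine dose. Specific Aim 2 compares the arms by the Aim 1 methods.

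**The concern.** The word that defines Primary Aim 1, efficacy, is attached in the modelling text to a set selected after randomisation. The apparent comparison is CHW receivers against an AE-C arm that is not selected in the same way. Families who take up home visits may differ in prognosis from those who do not, and the AE-C arm keeps its equivalents of both.

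Three choices are left open: the visit count that defines receipt, the AE-C counterpart, and the adjustment covariates. Each could be settled after the data are seen. If the per-protocol and ITT models disagree, nothing says which of the two is the primary model. The one listed first for efficacy lacks the protection of randomisation.

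**Working it through.** **1. What the exclusion requires.** Missing at random, in its usual sense, concerns outcomes that were not observed. Here some patients with observed outcomes are set aside because of something that happened after randomisation. Their removal is harmless only if receipt and outcome share no cause beyond the adjusted covariates.

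A simulation shows the difference: 94 per arm, SD 2.05, no true effect, no missing outcomes, about 22% non-receipt in the CHW arm, 4,000 replicates. Non-receipt depends on one measured and one unmeasured factor; the model adjusts for the measured one. All settings are assumptions.

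| Effect of unmeasured factor on outcome (days per SD) | Per-protocol bias (days) | Per-protocol rejection | ITT rejection |
|---|---|---|---|
| 0 | about 0 | 5.5% | 5.3% |
| 0.8 | -0.15 | 7.4% | 4.6% |
| 1.5 | -0.27 | 14.8% | 5.1% |

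**2. The plan's sample size.** Section 12.0 gives 2.84 against 2.0 days at 12 months, 80% power, 15% attrition and about 111 per group; Section 9.0 gives two-sided 0.05. The SD is not stated, so the figure can only be back-solved. Analysed per arm: 111 × 0.85 ≈ 94. Difference: 2.84 − 2.0 = 0.84 days. Power of 80% with 94 per arm then implies SD 2.045, and a standard error of the difference of 2.045 × √(2/94) = 0.298.

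**3. Illustrative bias, unadjusted t-test, no true effect.** Let q be the non-receipt share in the CHW arm. Assume the whole arm averages 2.84 days and non-receivers average 3.9, the baseline mean in Section 12.0. The receiver mean is (2.84 − 3.9q)/(1 − q), and the bias is 2.84 minus that. Receivers analysed number 94(1 − q), against 94 in AE-C.

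| q | Source | Receiver mean | Bias (days) | n | Two-sided rejection |
|---|---|---|---|---|---|
| 6.5% | 3/46 refused all visits, earlier programme, Section 2.0 | 2.766 | 0.074 | 88 vs 94 | 5.7% |
| 10% | assumed | 2.722 | 0.118 | 85 vs 94 | 6.7% |
| 20% | assumed | 2.575 | 0.265 | 75 vs 94 | 13.2% |

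Holding non-receivers at 3.9 widens the gap between them and receivers from 1.13 days at 6.5% (3.9 − 2.766) to about 1.33 at 20% (3.9 − 2.575). With the gap held at 1.13 days, q = 20% gives a bias of 0.20 × 1.13 = 0.23 days and a rejection rate of about 11%. Hence the range of 11% to 13%.

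**4. Power under ITT.** If the 0.84-day effect applies to receivers only, the ITT effect is 0.84(1 − q): 0.785, 0.756 and 0.672 days at 6.5%, 10% and 20%. With 94 per arm and SD 2.045, power is about 75%, 71% and 61%.

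**The case against.** The strongest reply is that the only stated success rule for activity days is the 12-month two-arm test, which is also the test that was powered. The mixed models come afterwards with no success criterion of their own, and an ITT version is already planned. This largely stands. A reader might infer that the trial's conclusion rests on the per-protocol model, or that no randomised comparison is planned; the documents support neither. What remains is that the rule's set is left implicit and that the efficacy label sits on the selected set.

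A reader might also take the per-protocol wording literally and conclude that the set contains no AE-C patients. The model includes treatment and treatment-by-time terms, which need both arms, so that reading does not hold.

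On missing at random, the sentence is conditional. If excluded patients' outcomes are treated as missing, the assumption given the covariates can be read as ignorable receipt. So the text is not plainly wrong, but claiming that unbiasedness is ensured is still too strong for an untestable condition and an unlisted set of covariates.

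On size, the effect is small at the only documented non-receipt figure. That figure counts outright refusals in a programme without a clinical partner; a minimum visit count could exclude more. The plan's model is covariate-adjusted, which could reduce the bias. Section 9.0 also expects more missing data among nonadherent patients, so fewer observed outcomes might be discarded than the illustration assumes.

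The ambiguity should not be stretched to Aim 3, where only the outcome measure is carried over from Aim 1.

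**Conclusion.** The point holds as one of priority and definition. The efficacy models start from a post-randomisation set without a receipt threshold, an AE-C counterpart or a covariate list. ITT is additional, and neither model set is primary. Followed as written, this can bias the efficacy estimate.

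The documents fix neither the size nor the direction of that bias; if non-receivers did better than receivers, it would reverse. The illustrative 0.07 days and 5.7% at 6.5% non-receipt, and 11% to 13% at an assumed 20%, rest on an SD that is not in the documents, an assumed prognosis for non-receivers and no covariate adjustment. They do not show that the trial's conclusion would be wrong. This should be fixed before analysis as a cheap improvement; it does not invalidate the design.

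**What to change.** In Section 9.0:

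- State that the success rule, the primary Aim 1 mixed model and the Aim 2 comparisons that follow Aim 1 use all randomised patients, analysed as assigned.
- Keep the per-protocol model as supportive. Define receipt in advance for both arms from the Section 6.6 encounter records, and list the adjustment covariates in advance.
- Reword the missing-at-random sentence so that lack of bias in the per-protocol model is conditional on no unmeasured common cause of receipt and outcome.

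The cost is wording only, since both analyses are already planned. The downside is that the ITT effect may be smaller than the effect in receivers: if 0.84 days applies to receivers only, power falls from 80% to about 75% at 6.5% non-receipt and about 61% at an assumed 20%.
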